8.5.2 SECONDARY ANALYSES

INO-4800	COVID19-311
Inovio Pharmaceuticals, Inc.	Clinical Protocol

8.5.2.1 Efficacy

Phase 3 Segment

The secondary efficacy incidence endpoints will be analyzed in the same manner as the primary hypothesis, but with 95% CIs and without the hypothesis test p-value.

8.5.2.2 Immunogenicity

Phase 3 Segment

Post-baseline increases from baseline in interferon- γ ELISpot response magnitudes will be compared between treatment groups using differences in medians and associated non-parametric 95% CIs.

Post-baseline increases from baseline in neutralizing antibody response titers will be compared between treatment groups using ratios of geometric mean fold-rises and associated t-distribution based 95% CIs.

The summaries listed above will be stratified according to disease status of the subjects and by baseline SARS-CoV-2 serostatus.

Valid samples for statistical analysis purposes will be those collected: at least 6 and no more than 30 days after Dose 2 for the Week 6 timepoint; at least 174 and no more than 198 days after Dose 2 for the Week 30 timepoint; and at least 356 and no more than 380 days after Dose 2 for the Week 56 timepoint... Baseline is defined as the last measurement prior to the first treatment administration.

The PP population will be used for these immunogenicity analyses.

8.5.3 SAFETY ANALYSES

8.5.3.1 Adverse Events

All AEs including injection-site reactions will be summarized among the Safety Population by frequency per treatment arm. These frequencies will be presented overall and separately by dose, and will depict overall, by system organ class and by preferred term, the percentage of subjects affected. Additional frequencies will be presented with respect to maximum severity and to strongest relationship to Study Treatment. Multiple occurrences of the same AE will be counted only once following a worst-case approach with respect to severity and relationship to Study Treatment. All serious AEs will also be summarized as above.

The main summary of safety data will be based on events occurring within 30 days of any dose. For this summary, the frequency of preferred term events will be compared between study arms with risk differences and 95% confidence intervals, using the method of Miettinen and Nurminen. As this analysis will use many event categories, and produce many confidence intervals, caution should be exercised when interpreting these confidence intervals. Separate summaries will be based on events occurring within 7 days of any dose and regardless of when they occurred.

The analyses listed above will be performed according to Phase. For the Phase 3 segment, the analyses listed above will also be performed according to SARS-CoV-2 serostatus at baseline.

For AE data, partial start dates will be imputed to the date of treatment to conservatively report the event as treatment-emergent, whenever the portion of the date is consistent with that of the study treatment. Otherwise, it will be imputed to the earliest date consistent with the partial date. A completely missing onset date will be imputed as the

INO-4800	COVID19-311
Inovio Pharmaceuticals, Inc.	Clinical Protocol

day of treatment. Partial stop dates will be assumed to be the latest possible day consistent with the partial date. AE duration will be calculated as (Stop Date – Start Date) + 1.

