- I. Subjects will be evaluated during a "COVID-19 assessment visit" when acute COVID-19 is suspected. The assessment visit may be performed in the clinic, subject's vehicle, or at a home visit and should be completed within 3 days of symptom onset or within 3 days of a positive result of a SARS-CoV-2 test.
- m. For subjects with confirmed SARS-CoV-2 infection during the trial, a convalescent visit should be scheduled approximately 28 days after symptom onset, or in the absence of symptoms, the date of positive SARS-CoV-2 test. If acute symptoms are ongoing the site should follow up with the subject via phone call or unscheduled visit after symptom resolution or stabilization
- n. Vital signs to be performed at COVID-19 assessment and convalescent visits include temperature, respiration rate, heart rate and oxygen saturation.
- o. Genotyping may also be performed on sample(s) collected at the COVID-19 assessment visit.
- p. Diaries to be used at selected sites only (estimated to include 711 subjects).
- q. Diary should be reviewed at the 14-day post-dose phone call or visit and collected at the next in-office visit.
- r. When possible, cellular and humoral immunology samples will be collected. Cellular samples will be collected at selected sites only.

INO-4800	COVID19-311
Inovio Pharmaceuticals, Inc.	Clinical Protocol

1.0 **INTRODUCTION**

This document is a protocol for a human research trial to be conducted according to U.S. and international standards of Good Clinical Practice (GCP) (FDA Title 21 part 312, 812 and International Conference on Harmonization (ICH) guidelines), applicable government regulations and Institutional research policies and procedures.

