Phase 3 Segment – Efficacy

In the Phase 3 segment, approximately 6714 seronegative and 402 seropositive subjects 18 years of age and older will be randomized at a 2:1 ratio to receive either active investigational product (INO-4800, 1mg) or placebo (SSC-0001). Approximately half of seronegative subjects and approximately half of seropositive subjects will be 18-50 years of age, and the other half will be \geq 51 years of age. Also, a minimum of 10% of the total sample size will be \geq 65 years of age.

Subjects will be randomized in a stratified manner according to (a) age category (18-50 years vs. ≥51 years) on Day 0, and (b) presence of or absence on Day 0 of any of the following underlying medical conditions that increase risk of severe COVID-19 disease, per CDC criteria [1], as listed below:

- Cancer
- Chronic kidney disease
- Chronic lung diseases, including Chronic obstructive pulmonary disease (COPD), asthma (moderate-to-severe), interstitial lung disease, cystic fibrosis, pulmonary hypertension
- Neurologic conditions including stroke or cerebrovascular disease, that do not impact cognition
- Diabetes (type 1 or type 2)
- Hypertension
- Heart conditions, such as heart failure, coronary artery disease, or cardiomyopathies
- HIV infection (CD4 count >200 cells/mm3 or undetectable viral load)
- Liver disease
- Obesity (BMI \geq 30 kg/m2)
- Sickle cell disease or thalassemia, or
- Smoking (current or former smoker).

This segment of the trial is case-driven. Among seronegative subjects, a total of 149 observed cases will be required for 90% power to declare the vaccine efficacious (>30%), assuming a true efficacy of 60%. A sample size of 6714 seronegative subjects is expected to be required to achieve the 149 cases assuming an underlying attack rate of 3.7%. The

INO-4800	COVID19-311
Inovio Pharmaceuticals, Inc.	Clinical Protocol

actual sample size may differ if the observed attack rate is different than projected. There are two formal interim analyses of efficacy; one when 50% of the cases accrue and one when 75% of the cases accrue. If the prespecified criteria for efficacy are met at either interim analysis, then enrollment will continue until 4500 subjects have been enrolled, and blinded follow-up will continue until at least those 4500 subjects have a minimum of 6 months of safety follow-up. At that point, the trial would be unblinded and placeborecipients will be offered the active product.

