3.4 SECONDARY ENDPOINTS

Table 7: Secondary Objectives and Associated Endpoints

Phase 2 Secondary Objectives | Phase 2 Secondary Endpoints

COVID19-311 Protocol | VV-TMF-00448 | 5.0

INO-4800	
Inovio Pharmaceuticals, Inc.	

COVID19-311 Clinical Protocol

1. Evaluate the safety and tolerability of INO-4800 administered by ID	1a. Incidence of solicited and unsolicited injection site reactions
injection followed immediately by EP	 Incidence of solicited and unsolicited systemic adverse events (AEs) by system organ class (SOC), preferred term (PT), severity and relationship to investigational product
	1c. Incidence of serious adverse events (SAEs)
	1d. Incidence of adverse events of special interest (AESIs)
Phase 3 Secondary Objectives	Phase 3 Secondary Endpoints
1. Evaluate the safety and tolerability of INO-4800	1a. Incidence of solicited and unsolicited injection site reactions
	 Incidence of solicited and unsolicited systemic adverse events (AEs) by system organ class (SOC), preferred term (PT), severity and relationship to investigational product
	1c. Incidence of serious adverse events (SAEs)
	1d. Incidence of adverse events of special interest (AESIs)
	1e. Incidence of all-cause mortality
2. Evaluate efficacy of INO-4800 in the prevention of COVID-19 disease according to degrees of disease severity in subjects who are SARS-	2a. Incidence of non-severe COVID-19 disease in SARS-CoV-2 seronegative subjects starting 14 days after completion of the 2-dose regimen until EOS
CoV-2 seronegative at baseline	2b. Incidence of severe COVID-19 disease in SARS- CoV-2 seronegative subjects starting 14 days after completion of the 2-dose regimen until EOS
	2c. Incidence of deaths due to COVID-19 in SARS- CoV-2 seronegative subjects starting 14 days after completion of the 2-dose regimen until EOS
3. Evaluate the cellular and humoral immune response to INO-4800	3a. Antigen-specific cellular immune response measured by IFN-gamma ELISpot
	3b. Neutralizing antibody response measured by a pseudovirus-based neutralization assay
4. Evaluate the efficacy of INO-4800 in the prevention of COVID-19 disease in subjects who are SARS- CoV-2 seropositive at baseline	 Incidence of virologically-confirmed COVID-19 disease starting 14 days after completion of the 2-dose regimen until 12 months post-dose 2 (End of Study (EOS)) in subjects who are SARS- CoV-2 seropositive at baseline

3.5 **EXPLORATORY OBJECTIVE**

See Table 8.

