3.8 SAFETY ASSESSMENT

Subjects will be followed for safety during the trial through scheduled clinic visits and phone calls. AEs, regardless of relationship to study drug, will be collected from the time of consent until 28 days post-dose 2 (i.e., Day 56). SAEs, MAAEs and AESIs will be collected from time of consent until EOS. SAEs, AESIs, and treatment-related AEs will be followed to resolution or stabilization. For the Phase 2 segment and at selected sites in the Phase 3 segment, solicited local and systemic AEs will be collected for 7 days following each dose using a participant diary.

Subjects will also be monitored for COVID-19 disease.

Please refer to the Schedule of Events (Table 3 and Table 4) for safety assessments to be performed.

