A negative result for urine β -HCG (test must have a sensitivity of at least 25 mlU/mL) must be available prior to each administration of IP. If the β -HCG test is positive, indicating that the subject is pregnant prior to completing the specified dose regimen, then no further IP will be administered. Every attempt should be made to follow pregnant subjects for the remainder of the study and to determine the outcome of the pregnancy (see Section 7.12).

DIARY

Diaries will be implemented in the Phase 2 segment of the protocol and at selected sites (estimated to include 711 subjects) in the Phase 3 segment. Subjects will be provided a diary to record the following solicited local and systemic AEs:

- Oral temperature and time taken (each daily entry before 11:59 pm)
- Solicited systemic symptoms
- Solicited local injection site symptoms
- Concomitant medications

The diary should be completed once daily starting the evening of each study dose through 6 days post-dose. The completed diary post-dose 1 and post-dose 2 will be reviewed with the subject by the study staff during the next study phone call or visit and collected at the next in-person study visit. The study staff will review the diary with the subject to assess for temperature, solicited systemic symptoms (unusually tired/feeling unwell, muscle aches, headache, nausea, joint pain) and solicited injection site symptoms (pain, itching, redness, swelling, bruising). In addition, unsolicited symptoms and concomitant medications will be assessed.

Any diary entry determined to meet the Common Terminology Criteria for Adverse Events version 5.0 (CTCAE) criteria for a Grade 1 or higher adverse event should be documented as an adverse event unless deemed part of the subject's ongoing medical history. Injection site reactions should be graded per the Toxicity Grading Scale for Healthy Adult and Adolescent Volunteers Enrolled in Preventive Vaccine Clinical Trials, issued September 2007 (See Section 6.4.5). If the diary entry does not meet the criteria of a Grade 1 or higher AE as per the relevant guidelines, Investigator clinical judgment can be used to determine whether the entry should be recorded as an AE and documented accordingly in the site's source. For cases where the diary entry and final AE reporting (i.e. grading) do not agree, the reasoning should be recorded in the source documents.

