8.4 ANALYTICAL POPULATIONS

Analysis populations will be:

The per-protocol (PP) population includes all subjects who receive all doses of Study Treatments and have no protocol violations. Subjects in the PP population will be grouped to treatment arms as randomized. Subjects excluded from the PP population will be identified and documented prior to unblinding of the trial database. Analyses on the PP population among those who are baseline SARS-CoV-2 seronegative will be primary for the analyses of efficacy in the Phase 3 segment of this trial.

The modified intention to treat (mITT) population includes all subjects who receive at least one dose of Study Treatment. Subjects in this population will be grouped to treatment arms as randomized. Analysis of the mITT population will be considered supportive for the corresponding PP population for the analyses of efficacy in the Phase 3 segment of this trial.

The intention to treat (ITT) population includes all subjects who are randomized. Subjects in this sample will be grouped to treatment arms as randomized. Analysis of the ITT population will be considered supportive for the corresponding PP population for the analyses of efficacy in the Phase 3 segment of this trial.

The safety analysis population includes all subjects who receive at least one dose of Study Treatment. Subjects will be analyzed according to the treatments received.

8.5 **DESCRIPTION OF STATISTICAL METHODS**

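### Phase 3 solicited reactions come from diaries in about 10% of subjects, but Section 8.5.3.1 reports them as a percentage of the whole Safety Population

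*Protocol*

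**What the plan says.** All references are to version 5.0 of the protocol.

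- **Collection.** Section 3.8 says that, besides Phase 2, "at selected sites in the Phase 3 segment, solicited local and systemic AEs will be collected for 7 days following each dose". The instrument is a diary that the subject keeps. The Diary paragraph of Section 6.4 places the diaries "at selected sites (estimated to include 711 subjects) in the Phase 3 segment", and a footnote to the Phase 3 Schedule of Events (Table 4) repeats this: "Diaries to be used at selected sites only (estimated to include 711 subjects". Section 6.4 also has diary entries of Grade 1 or higher documented as adverse events, unless they belong to the subject's ongoing medical history.
- **Endpoints.** Phase 3 secondary endpoint 1a in Table 7 (Section 3.4) is "Incidence of solicited and unsolicited injection site reactions". Endpoint 1b is the systemic counterpart.
- **Size.** Section 3.0 plans that "approximately 6714 seronegative and 402 seropositive subjects 18 years of age and older will be randomized at a 2:1 ratio".
- **Analysis.** Section 8.5.3.1: "All AEs including injection-site reactions will be summarized among the Safety Population by frequency per treatment arm", showing "by system organ class and by preferred term, the percentage of subjects affected". Section 8.4 defines the denominator: "The safety analysis population includes all subjects who receive at least one dose of Study Treatment". The additional 7-day summary in Section 8.5.3.1 follows the same rule and names no diary subset. No solicited-event population is defined.
- **Subjects without a diary.** Section 6.4.5 has every subject observed for 30 minutes after administration. Section 6.4.4 has every subject asked about adverse events, including injection-site reactions, at visits and calls.

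**The concern.** A percentage of subjects with a solicited reaction means something only among subjects in whom the reaction was solicited. In Phase 2 every subject has a diary, so the Safety Population is the right denominator there. Version 5.0 added diaries to Phase 3 at selected sites only. The adverse-event analysis gained a breakdown by baseline serostatus but no matching denominator.

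Taken as written, the Phase 3 table puts diary-recorded reactions and later-recalled reactions into one numerator and divides by everyone dosed. The result estimates neither the diary rate nor the rate found by asking. At stake are the solicited parts of secondary endpoints 1a and 1b, and the Miettinen-Nurminen risk differences for the same preferred terms. Dilution pulls those differences toward zero, which for safety is the less cautious direction. Phase 3 rates would also not be comparable with the Phase 2 rates from the same trial.

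**Working it through.** **Inputs from the protocol.** Phase 3 cells in Table 2: 4476 + 268 on INO-4800 and 2238 + 134 on placebo. Diary subjects: about 711.

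**The plan's own figures.** 4476 + 268 + 2238 + 134 = 7116, of whom 4744 are on INO-4800 and 2372 on placebo. 10% of 7116 is 711.6, which agrees with the stated 711. The diary share is f = 711/7116 = 0.0999.

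**When subjects without a diary are asked.** The diary runs from the evening of dosing through 6 days after it.

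- After Dose 1, the first scheduled contact is the Day 14 call (±3 days), so no earlier than Day 11. The Day 28 visit follows.
- After Dose 2, the first is the Day 42 visit, which Table 4 requires to be at least 10 days after the Day 28 visit.

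Apart from the 30-minute observation, all scheduled questioning therefore falls after the 7-day window has closed. Capture is above zero, but it depends on recall or on the subject reporting unprompted.

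**Dilution formula.** Let c be the share of reactions reaching the adverse-event data in subjects without a diary, relative to diary capture. Then

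reported % = true % × [f + (1 − f)c] = true % × [0.0999 + 0.9001c],

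and the understatement is 1/(0.0999 + 0.9001c). The documents give no value for c, so the whole range is shown, with an assumed true rate of 30%:

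| c (assumed) | Reported rate | Understatement |
|---|---|---|
| 0 | 3.0% | 10.0-fold |
| 0.25 | 9.8% | 3.1-fold |
| 0.5 | 16.5% | 1.8-fold |
| 0.75 | 23.3% | 1.3-fold |
| 1 | 30.0% | 1.0-fold |

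**Risk differences.** If c is the same in both arms, the difference shrinks by the same factor. A true 30% against 15% (15 points) becomes 15 × 0.0999 = 1.5 points at c = 0 and 15 × 0.55 = 8.3 points at c = 0.5.

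**Interval width.** This uses a Wald approximation as a rough stand-in for Miettinen-Nurminen. At c = 0.5 the full table compares 16.5% of 4744 with 8.25% of 2372:

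1.96 × √(0.165 × 0.835/4744 + 0.0825 × 0.9175/2372) = 0.015.

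The interval is about 6.7 to 9.8 points and excludes the true 15.

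If 2:1 allocation holds at diary sites, the diary subset has 711 × 2/3 = 474 and 711/3 = 237 subjects:

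1.96 × √(0.30 × 0.70/474 + 0.15 × 0.85/237) = 0.061.

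That gives 15 ± 6.1 points, which is wider but centered on the right quantity.

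**The case against.** The strongest reply is that subjects without a diary are not left to report spontaneously. They are observed for 30 minutes, asked directly about injection-site reactions, and contacted on Days 14, 28 and 42. This stands. A reader might infer from 711 of 7116 that the table understates reactogenicity ten-fold. That would need zero capture in about 6,400 subjects who are questioned several times, and the documents do not support it. Ten is a ceiling, and the actual factor cannot be derived from the protocol.

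A reader might also infer that endpoints 1a and 1b are wrong as a whole, or that one arm gains. Neither follows. Both endpoints also cover unsolicited events, for which the Safety Population is the proper denominator. Diaries are assigned by site, not by arm, so dilution is not differential by design. These summaries carry no formal hypothesis, Section 8.5.3.1 itself advises caution with the intervals, and Phase 2 will supply undiluted diary rates, including about 150 subjects at 1.0 mg.

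The last reply is that a solicited-event set is often left to a separate statistical analysis plan, which is not at hand. That carries less weight here. Section 8.1 calls these sections the formal Statistical Analysis Plan, and Section 8.5.3.1 does state a denominator. A separate plan using diary subjects would depart from that text.

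**Conclusion.** The point holds in limited form and should be fixed, although it does not threaten the trial's main conclusions. The stated rule divides diary-collected reactions from about 10.0% of Phase 3 subjects by everyone dosed. Solicited incidence is understated, and risk differences are shrunk toward zero, by 1/(0.10 + 0.90c): somewhere between 1-fold and 10-fold, and 1.8-fold if subjects without a diary yield half the reactions.

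This rests on four assumptions: about 711 diary subjects are realized; nearly all randomized subjects are dosed; 2:1 allocation holds at diary sites; and c is similar in the two arms, which blinding makes plausible but does not guarantee. Contact timing makes c = 1 unlikely for mild, short-lived reactions, but the documents do not fix its value. No efficacy conclusion changes.

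**What to change.** In Section 8.5.3.1, add that Phase 3 solicited local and systemic reactions within 7 days of each dose are summarized by arm and by dose, with the denominator being subjects who received that dose and were issued a diary. Compute the risk differences for solicited terms on the same set.

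Keep the full Safety Population for unsolicited AEs, MAAEs, AESIs and SAEs. For the terms listed in the diary, show results separately for diary and non-diary sites. Do not drop those terms from the full-population tables, because that would discard valid queried events from about 90% of subjects.

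The change uses data already planned and needs one set definition and revised table shells, settled before unblinding. The cost is precision: solicited events would rest on about 474 against 237 subjects instead of 4744 against 2372, so their intervals widen.

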Physical Exam ^b	Х	Х			Х		Х		Х		Х		Х		Х	Х	Х
Vital Signs	Х	Х			Х		Х		Х		Х		Х		Х	X ⁿ	Xn
Height and Weight	Х																
HIV Serology		Х															
Pregnancy Test ^c	Х	Х			Х												
INO-4800 or Placebo + EP ^d		Х			Х												
Download EP Data ^e			Х			Х											
Adverse Events ^f	Х	Х	Х	Х	Х	Х	Х	Х	Х	Х	Х	Х	Х	Х	Х	Х	Х
Cellular Samples ^g		Х					Х				Х				Х	Xr	Х
Humoral Samples ^h		Х					Х				Х				Х	Xr	Х
SARS-CoV-2 Serology ⁱ	Х	Х			Х		Х		Х		Х		Х		Х		Х
SARS-CoV-2 RT-PCR		х														X٥	
(Nasopharyngeal swabs)		^														^	
Distribute Diary ^p			Х			Х											
Review/Collect Diary ^q				Х	Х		Х										

a. Screening assessment occurs from -30 days to -1 day of Day 0. Screening and Day 0 visits may be combined if eligibility is able to be confirmed prior to dosing. If so, all assessments for Screening and Day 0 must be performed at the combined visit.

b. Full physical examination only at Screening and Day 393 (or EOS). Targeted physical exam at other indicated visits.

COVID19-311 Protocol | VV-TMF-00448 | 5.0

INO-4800 Inovio Pharmaceuticals, Inc.

COVID19-311 Clinical Protocol

- c. In women of childbearing potential. Urine pregnancy test at all indicated visits.
- d. Intradermal injection(s) in skin preferably over deltoid region, or alternately over anterolateral quadriceps region, followed by EP at Day 0 and Day 28.
- e. Following administration of INO-4800 or placebo, EP data will be downloaded from the CELLECTRA® 2000 device and provided to Inovio.
- f. AEs to be collected from time of consent to Day 56; SAEs, MAAEs, and AESIs to be collected from time of consent to EOS.
- g. On Day 0, cellular sampling requires 64 mL of whole blood prior to 1st dose. At all other time points, collect 32 mL of whole blood. Cellular samples will be collected at selected clinical sites (estimated to include 711 subjects)
- h. On Day 0, humoral sampling requires a total of 17 mL of whole blood (two 10-mL red top serum collection tubes, each 8.5 mL of whole blood, to produce four serum aliquots of 2 mL each). At all other time points, collect 8.5 mL of whole blood in a single 10-mL red top serum collection tube to produce two serum aliquots of 2 mL each.
- i. SARS-CoV-2 antibody.
- j. The Day 0 RT-PCR results will not be required prior to dosing on that day.
- k. Day 42 visit must occur at least 10 days after Day 28 visit.

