6.1.1.1 Medical History

A medical history will be obtained by the Investigator or qualified designee at the time of Screening. Medical history will include all active conditions, and any other past conditions, as well as surgical procedures, that are considered to be clinically significant by the Investigator and/or having occurred within 3 months prior to Screening. Subjects should be queried about any history of Hepatitis B, Hepatitis C and HIV.

In the Phase 3 segment, subjects with a self-reported history of Hepatitis B or C must provide documentation of liver enzymes that are not significantly elevated within the past 3 months. If such a report of liver enzyme testing is not available, this testing should be performed at Screening. Subjects with a history of Hepatitis C without cirrhosis who have completed treatment and have proof of an undetectable viral load at least 12 weeks following treatment may be enrolled and do not require liver enzymes within the past months.

Subjects with self-reported HIV must provide documentation of controlled HIV infection based on a CD4 count greater than 200 cells/mm³ or an undetectable viral load within the past 3 months. If a recent CD4 count and/or viral load is not available, this testing should be performed at Screening.

Illnesses first occurring or detected after the signing of the informed consent, or during the study and/or worsening of an existing illness in severity, frequency or nature after signing of the informed consent are to be documented as AEs on the Case Report Forms (CRF). Prior treatments, defined as administered up to 12 weeks prior to the time of informed

INO-4800	COVID19-311
Inovio Pharmaceuticals, Inc.	Clinical Protocol

consent and stopped prior to dosing on Day 0, should be recorded in the CRF as prior medications. Concomitant treatments, defined as continuing on Day 0 or new treatments taken at or after Day 0, should be recorded in the CRF as concomitant medications.

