6.4.4 ASSESSMENT OF CLINICAL TRIAL ADVERSE EVENTS (AES)

Subjects will be queried regarding the occurrence of any AEs including AEs related to injection site reactions, concomitant medications and new onset illness or disease during their study visits and phone calls. Subjects will be reminded to contact study personnel and immediately report any event for the duration of the study. All AEs will be captured from the time of the informed consent until 28 days post-dose 2 (Day 56). Following the Day 56 visit, only SAEs, AESIs and MAAEs will be collected. All related AEs, AESIs and SAEs will be followed to resolution or stabilization. These events will be recorded on the subject's CRF.

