7.2 ADVERSE EVENTS (AES)

Any untoward medical occurrence in a patient or clinical investigation subject administered a pharmaceutical product and which does not necessarily have a causal relationship with this treatment.

An AE can therefore be any unfavorable and unintended sign (including an abnormal laboratory finding, for example), symptom, or disease temporally associated with the use of a medicinal product, whether or not considered related to the medicinal product.

Adverse Events (AEs) include the following:

- Pre- or post-treatment complications that occur as a result of protocol mandated procedure during or after screening (before the administration of clinical trial drug);
- Any pre-existing condition that increases in severity, or changes in nature during or as a consequence of the clinical trial drug administration phase;
- Complications of pregnancy (refer to Section 7.11).

Adverse Events (AEs) do not include the following:

- Medical or surgical procedures (e.g., surgery, endoscopy, tooth extraction, transfusion) performed; however, the condition that leads to the procedure is an AE;
- Pre-existing diseases or conditions or laboratory abnormalities present or detected before the Screening Visit that do not worsen;
- Situations where an untoward medical occurrence has not occurred (e.g., hospitalization for elective surgery, social and/or convenience admissions);
- Overdose without clinical sequelae;
- Any medical condition or clinically significant laboratory abnormality with an onset date before the ICF is signed, is not an AE; it is considered to be pre-existing and will be documented on the medical history CRF;
- Uncomplicated pregnancy;
- An induced elective abortion to terminate a pregnancy without medical reason;

INO-4800	COVID19-311
Inovio Pharmaceuticals, Inc.	Clinical Protocol

• Confirmed COVID-19 disease.

7.3 **ADVERSE DRUG REACTION (ADR)**

All noxious and unintended responses to a medicinal product related to any dose. This means that a causal relationship between the medicinal product and an adverse event is at least a reasonable possibility (i.e., the relationship cannot be ruled out).

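### AE date rules in Protocol 8.5.3.1 can count events that ended before dose 1 as treatment-emergent, and one AE summary has no lower bound at dose 1; the effect is small and favours neither arm

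*Protocol*

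**What the plan says.** Section 8.5.3.1 tabulates all AEs of the Safety Population by arm. Section 8.4 defines that population by the subject (at least one dose received), not by the timing of the event. The main summary takes events within 30 days of any dose and compares preferred terms by risk differences with Miettinen-Nurminen intervals. It then adds: "Separate summaries will be based on events occurring within 7 days of any dose and regardless of when they occurred".

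On incomplete dates, the same section says that "partial start dates will be imputed to the date of treatment to conservatively report the event as treatment-emergent". The only condition is that the known part of the onset date agrees with the treatment date; otherwise the earliest consistent date is used. A completely missing onset becomes the day of treatment without any condition. Partial stop dates go to the latest possible day, and a complete stop date stays as recorded. Duration is stop date minus start date plus one.

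On collection, footnote f of Table 4 (Phase 3 Schedule of Events) reads "AEs to be collected from time of consent to Day 56; SAEs, MAAEs, and AESIs to be collected from time of consent to EOS". Footnote a reads "Screening assessment occurs from -30 days to -1 day of Day 0", and also "Screening and Day 0 visits may be combined if eligibility is able to be confirmed prior to dosing". Section 6.1.1.1 records as AEs "Illnesses first occurring or detected after the signing of the informed consent", and section 7.2 lists complications of screening procedures before administration among AEs. Section 8.1 describes section 8 as the formal statistical analysis plan.

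**The concern.** Two rules place pre-vaccine events in the columns of the arms.

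First, the imputation is presented as conservative. That is fair when the timing of an event is unknown. It is not fair when the recorded stop date shows that the event was over before the first dose. The rule then overrides known information and contradicts the duration formula in the same paragraph. The misplaced event also reaches the main between-arm comparison.

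Second, the summary without a time limit is the only stated one that extends more than 30 days past a dose, so it is the one that covers SAEs, AESIs and MAAEs to the end of the study. It starts at consent, not at dose 1. The idea of a treatment-emergent event appears in 8.5.3.1 only as the purpose of the imputation; it is not defined there and restricts no table. Because repeated occurrences of an AE count once at worst severity and strongest relationship, a pre-dose episode can by itself mark a subject as affected or set the severity shown.

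At stake is whether the AE tables can be read as events after vaccination.

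**Working it through.** The protocol gives no figure on this point to reproduce. The check has three parts.

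**1. Imputation against the stop date.** Take the treatment date as dose 1; with two dosing dates the text does not say which is meant. The dates below are an assumed example.
- Onset recorded as June 2021, stop 5 June 2021, dose 1 on 20 June 2021.
- The known part (June 2021) fits the dose date, so the onset becomes 20 June.
- Days from dose to imputed onset: 0. The event enters the 7-day and the 30-day windows.
- Duration = stop - start + 1 = 5 - 20 + 1 = -14 days.

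In general, with dose on day D of a month and stop on an earlier day s of that month, duration = s - D + 1. The largest value is at s = D - 1, giving 0. The smallest in a 30-day month is at D = 30, s = 1, giving -28. It is never positive. For a completely missing onset the month need not match: a stop at Day -30 gives -30 - 0 + 1 = -29.

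**2. Pre-dose share of collection time.** Inputs: 0 to 30 days before Day 0 (Table 4, footnote a); Day 56 and end of study (footnote f); end of study at Day 393.
- AEs collected only to Day 56, share = pre/(pre + 56): same-day screening 0/56 = 0%; 7 days 7/63 = 11%; 14 days 14/70 = 20%; 30 days 30/86 = 35%.
- SAEs, AESIs and MAAEs, maximum share: 30/(30 + 393) = 30/423 = 7%.

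**3. Effect on a comparison.** Let pv and pc be the true post-dose risks of a term and q the pre-dose risk, equal in both arms and independent of the post-dose risk. If pre-dose events count, the observed risks are 1 - (1 - pv)(1 - q) and 1 - (1 - pc)(1 - q). Their difference is (1 - q)(pv - pc), so the risk difference shrinks by exactly the factor 1 - q. All risks below are assumptions.
- pv = 10%, pc = 5%, q = 3%: observed 1 - 0.90 x 0.97 = 12.7% and 1 - 0.95 x 0.97 = 7.85%. The risk difference goes from 5.0 to 4.85 points and the ratio from 2.0 to 1.62.
- Constant background rate, c over 56 days in placebo, true ratio 2, 30 pre-dose days, q = 1 - (1 - c)^(30/56):

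| c | q | Risk difference, true | Risk difference, observed | Ratio observed |
|---|---|---|---|---|
| 2% | 1.08% | 2.0 points | 1.98 points | 1.65 |
| 5% | 2.71% | 5.0 points | 4.86 points | 1.64 |
| 10% | 5.49% | 10.0 points | 9.45 points | 1.63 |

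- Events followed to Day 393, c = 5% over 393 days, true ratio 2: q = 1 - 0.95^(30/393) = 0.39%. The risk difference goes from 5.0 to 5.0 x 0.9961 = 4.98 points, and the ratio reads 1.93.

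Part 3 describes the summary without a time limit. The main 30-day summary is exposed only through part 1, and the protocol gives no basis for estimating how often that occurs.

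**The case against.** **Only the 30-day summary carries a planned comparison, and it uses risk differences.** This stands. No AE risk ratio is planned, and the summary without a time limit is descriptive. A reader might infer from the table above that relative comparisons in the long-term safety table would drop from 2.0 to about 1.6. The documents plan no such comparison, and that figure belongs to AEs collected only to Day 56 with the full 30 days of screening.

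**The arms are balanced before dosing.** This stands. Subjects are randomized at the Day 0 visit (section 6.1.2.1) and the Phase 3 segment is double-blind, so pre-dose events fall equally on the arms in expectation. A reader might infer a bias for or against the vaccine; nothing in the documents supports one.

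**The windows are tied to a dose, so the natural reading is after that dose.** This stands. The text does not state a direction, and a literal reader might take the main window to include the 30 days before a dose. With treatment-emergence named as the purpose of the imputation, that reading is not well supported, and the point does not rest on it.

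**The imputation problem is a corner case.** This stands in part. It needs an incomplete onset date and a stop date known to precede dose 1, and AEs are elicited at Screening and again before dosing on Day 0, which makes unknown onsets less likely. It is not confined to onset and dose in the same month, because a completely missing onset is moved without any condition. Rarity does not make the rule right where it applies.

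**These details belong in a statistical analysis plan.** This is weak here. Only the protocol was available and a separate plan may exist, but section 8.1 calls section 8 the formal plan, and the point concerns rules that it states, not detail left open.

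**Conclusion.** The point holds as a minor one. As written, the imputation rule classes an event known to have ended before dose 1 as treatment-emergent, places it in the 7-day and 30-day summaries, including the main risk-difference comparison, and gives it a duration of zero or less. This follows from the text and needs no assumption beyond an incomplete onset date and a recorded earlier stop date. In addition, the summary without a time limit tabulates pre-vaccine events under the arms, because collection starts at consent.

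The size is small and without direction. The pre-dose share of collection time is 0 to 35% for AEs collected only to Day 56; 35% requires the full screening period, and Phase 3 allows same-day screening. It is at most about 7% for SAEs, AESIs and MAAEs. A reader might carry the 35% over to the long-term table of serious and special-interest events; the collection periods do not allow that. Under the assumed risks with 30 pre-dose days, risk differences shrink by about 1 to 6% of their value. These figures assume equal pre-dose risk in both arms and independence from post-dose risk. The number of events with incomplete onset dates is unknown.

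**What to change.** Add two statements to section 8.5.3.1:

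1. An imputed onset date may never be later than the recorded stop date, and an event that stopped before dose 1 is classed as pre-dose.
2. The AE summaries by arm, including the one without an upper time limit, count events with onset or worsening on or after dose 1; events before dose 1 are listed separately.

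The pre-dose share in the by-arm tables then falls to 0%, and the imputation no longer produces durations of zero or less. Pre-dose events stay visible in their own listing, so nothing collected is lost. The cost is minor programming work; data collection does not change.
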